#### **11.5. Planned Statistical Models for PK Parameters and Concentrations**

No formal statistical analysis is planned for ME3183 and its metabolite (CCI [REDACTED]) concentrations.

#### **11.6. Interim Analyses**

[figure not shown]
No formal interim analysis is planned.

#### **11.7. Deviation from Analyses Planned in Protocol**

Not applicable.

This document is confidential.

CCI

This document is confidential.

## 13. Safety

All safety analyses will be performed using the safety analysis set.

### 13.1. Adverse Events

An AE is any symptom, physical sign, syndrome, or disease that either emerges during the study or, if present at Screening, worsens during the study, regardless of the suspected cause of the event. AEs will be collected from the time the subject signs the ICF through 4 weeks after the last dose of study drug.

AEs will be coded according to the MedDRA Version 24.1 or higher. Unless otherwise specified, AEs will be summarized by SOC and PT by treatment group and overall, with SOCs presented in the standard international order and PTs within SOCs presented in descending order of subject incidence.

Adverse events are summarized by subject incidence rates. In any tabulation, a subject contributes only once to the count for a given SOC or PT. If a subject experiences more than 1 occurrence of the same AE, the occurrence with the greatest severity and the closest association with the study drug will be used in the summary tables.

For the purposes of this study, any AEs classified as 'Unrelated' or 'Unlikely' will be considered as 'Not Related' and 'Possibly', 'Probably', or 'Definitely' as 'Related' to the study treatment. Missing relationship will be considered related to study product.

All AEs will be listed by subject, along with information regarding onset, duration, relationship and severity to study drug, seriousness, action taken with study drug, and outcome.

#### 13.1.1. Treatment-Emergent Adverse Events

A Treatment-Emergent Adverse Event (TEAE) is an AE that occurred during the study after the first dose of study drug or that was present prior to dosing and exacerbates after the first dose of study drug.

If the treatment-emergent status of an AE is unclear due to a missing/incomplete start date, it will be considered treatment-emergent. Date imputation rules for missing AE start dates are described in [Section 8.3](#).

#### 13.1.2. Overall summary of AEs

An overall summary of the following AE categories will be provided for all subjects in the Safety Analysis Set:

- Any AEs
- Any TEAEs
- Any drug-related TEAEs
- Any severe TEAEs
- Any serious TEAEs
- Any serious drug-related TEAEs
- Any TEAEs leading to treatment discontinuations
- Any serious TEAEs leading to treatment discontinuation
- Any TEAEs leading to death
- Any deaths

This document is confidential.

### 13.1.3. TEAEs by Maximum Severity/Relationship

All TEAEs will be summarized by maximum severity (mild, moderate, severe, and, if needed, missing). If a subject reports multiple occurrences of a specific event within a specific analysis period, the subject will be counted only once by the maximum severity. If the severity is missing for one or more but not all of the occurrences of the same event, the maximum severity of the remaining occurrences with non-missing severities will be used. If the severity is missing for all of the occurrences, the subject will be counted only once in the “missing” category of severity.

Similarly, all TEAEs will be summarized by maximum relationship to the study drug (unrelated, unlikely, possibly, probably, definitely related, and missing if needed). If a subject reports multiple occurrences of a specific event within a specific analysis period, the subject will be counted only once by the maximum relationship. If the relationship is missing for one or more but not all of the occurrences of the same event, the maximum relationship of the remaining occurrences with non-missing relationships will be used. If the relationship is missing for all of the occurrences, the subject will be counted only once in the “missing” category of relationship to the study drug.

### 13.1.4. TEAEs by Time of Onset

All TEAEs will be summarized by time of onset (Day 1 – 3, Day 4 – 7, Day 8 – 14, Day 15 – 21, Day 22 – 28, Day 29 – 56, Day 57 – 84, Day 85 – 113, Day 114+), where an overall summary of the numbers and percentages of subjects with any TEAEs within a particular time of onset period will be calculated along with further breakdown by SOC and PT.

## 13.2. Laboratory Evaluations

Laboratory tests include the following:

- Viral serology (HBV, HCV, and HIV)
- Hematology and coagulation
- Blood chemistry
- Urinalysis (Dipstick)
- Pregnancy tests (WOCBP only; serum or urine  $\beta$ -human chorionic gonadotropin)
- Serum follicle-stimulating hormone (FSH) (postmenopausal women only)

Summary statistics of actual values and changes from baseline will be provided for each laboratory parameters by treatment group at each study visit if the results of the laboratory are continuous. Frequencies tables, including numbers and percentages of subjects with normal and abnormal (low vs high), will be presented for laboratory parameters with categorical results by treatment group at each study visit. Shift tables will also be provided displaying the numbers and percentages of subjects with normal and abnormal results compared with the results at baseline.

Viral serology and pregnancy test results will be summarized in listings only. Subject data listings of all laboratory data will be provided.

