5.2.2 Clinical Studies

Two (2) Phase 1 studies in healthy adult subjects (ME3183-1 and ME3183-2 studies) have been conducted and 126 individuals who received study treatment (96 subjects received ME3183 and 30 subjects received placebo). ME3183 was tolerable and safe in healthy adults up to 25 mg single administration, and 10 mg twice daily (BID) and 15 mg QD for 14 days multiple administrations. Frequently reported treatment-emergent adverse events (TEAEs), the TEAEs reported by more than 2 subjects, in single administration were diarrhea, headache, lipase increased, tachycardia, and nausea. The majority of TEAEs in single ascending dose (SAD) studies were classified as mild. Most of the TEAEs were recovered/resolved within few days without any medication. The serious adverse event (SAE) of severe vasovagal neurocardiac syncope occurred in 12.5 mg subject. When ME3183 were administered repeatedly, the frequently reported TEAEs were; medical device site reaction, headache, diarrhea, abdominal pain, vomiting, nausea, hematochezia, back pain, arthralgia, pain in extremity, myalgia, dermatitis, decreased appetite, and dysmenorrhea. The majority of TEAEs in multiple ascending dose (MAD) study were classified as mild. All TEAEs were temporal and resolved during the dosing period. No SAE was occurred in MAD study.

ME3183 was administered to healthy adult subjects in either in suspension (1 mg to 12.5 mg) or capsule (12.5 mg to 25 mg) in SAD studies. ME3183 was absorbed orally in both form with peak concentration recorded at approximately 3.5 hours to 4 hours postdose and was eliminated slowly with an elimination half-life ($t_{1/2}$) of approximately 16 hours to 24 hours. The means of C_{max} and AUC increased slightly greater than a dose proportionality from 1 mg to 10 mg suspension, while C_{max} and AUC increased almost dose proportionally over the dose range of 12.5 mg to 25 mg of capsule administration. The means of C_{max} and AUC in CCI [REDACTED] (metabolite of ME3183) were approximately from [REDACTED] % to [REDACTED] % compared with those of ME3183 at each dose level. As the dose of ME3183 increases, the ratio of C_{max} and AUC of CCI [REDACTED] to ME3183 tended to decrease. The mean of cumulative urinary excretion rate in ME3183 was [REDACTED] % to [REDACTED] % which was quite small.

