25. Subject has received any systemic immunosuppressants (eg, methotrexate, azathioprine, cyclosporine, 6-thioguanine, mercaptopurine, mycophenolate mofetil, hydroxyurea, tacrolimus), any protein kinase inhibitor (eg, tofacitinib, baricitinib, peficitinib, upadacitinib), or anakinra within 4 weeks of the first administration of study treatment.
26. Subject has received phototherapy (eg, ultraviolet B including narrow band ultraviolet B, Goeckerman therapy, and excimer laser or psoralen ultraviolet A) or any systemic medications/treatments that could affect psoriasis or sPGA evaluation (including, but not limited to, oral or injectable corticosteroids, retinoids, 1,25-dihydroxy vitamin D3 and analogues, psoralens, sulfasalazine, or fumaric acid derivatives) within 4 weeks of the first administration of study treatment.
27. Subject has had a recent initiation of a drug that is known to potentially cause or exacerbate psoriasis (including, but not limited to, beta-blockers, lithium, and anti-malarials) within the 8 weeks prior to the first administration of study treatment; a subject who has been on a stable dose for at least 8 weeks prior to the first administration of study treatment without exacerbation of psoriasis may be randomized and does not need to discontinue these medications.
28. Subject has used topical medications/treatments that could affect psoriasis or sPGA evaluation (including, but not limited to, corticosteroids, anthralin, calcipotriene, topical vitamin D derivatives, retinoids, tazarotene, methoxsalen, trimethylpsoralen, pimecrolimus, tacrolimus, or PDE4 inhibitor) within 2 weeks of the first administration of study treatment.

29. Subject has received an investigational drug for biologic therapy within the previous 24 weeks prior to the first administration of study treatment or received any other non-biologic investigational therapy/drugs or device within 4 weeks or 5 half-lives (whichever is longer) prior to the first administration of study treatment.
30. Subject has received any prior treatment with ME3183.
31. Subject has any of the following abnormal laboratory test findings at Screening.
 - Abnormal hepatic function
 - Aspartate aminotransaminase or alanine aminotransaminase $\geq 2 \times$ upper limit of normal or
 - Total bilirubin $\geq 2 \times$ upper limit of normal, unless the subject has a diagnosis of Gilbert's syndrome
 - White blood cell count $< 3000/\text{mm}^3$ ($< 3.0 \times 10^9/\text{L}$)

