## 8. General Aspects for Statistical Analysis

### 8.1. General Methods

- Unless otherwise specified, summaries will be presented for each treatment group and overall.
- Continuous variables will be summarized using the number of subjects (N), mean, standard deviation (SD), median, minimum, and maximum. Categorical variables will be tabulated with the number and percentage of subjects for each category.
- All relevant subject data will be included in listings. All subject data will be included in listings. The listings will be generally sorted by treatment and subject identification (ID), unless otherwise specified.

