14.3.1.7	Treatment-Emergent Adverse Events Leading to Permanent Discontinuation of Study Drug by System Organ Class and Preferred Term	(Safety Analysis Set)
14.3.1.8	Treatment-Emergent Adverse Events by Time of Onset, System Organ Class and Preferred Term	(Safety Analysis Set)

This document is confidential.

Table Number	Name	Analysis Set
14.3.2.1	Serious Treatment-Emergent Adverse Events, Listing	(Safety Analysis Set)
14.3.2.2	Treatment-Emergent Adverse Events Leading to permanent Discontinuation of Study Drug, Listing	(Safety Analysis Set)
14.3.4.1.1.1	Hematology and Coagulation: Summary by Visit and Change from Baseline	(Safety Analysis Set)
14.3.4.1.1.2	Hematology and Coagulation: Proportion of Abnormal Results by Study Visit	(Safety Analysis Set)
14.3.4.1.2.1	Blood Chemistry: Summary by Visit and Change from Baseline	(Safety Analysis Set)
14.3.4.1.2.2	Blood Chemistry: Proportion of Abnormal Results by Study Visit	(Safety Analysis Set)
14.3.4.1.3	Urinalysis: Proportion of Abnormal Results by Study Visit	(Safety Analysis Set)
14.3.4.2	Summary of Vital Signs by Visit and Change from Baseline	(Safety Analysis Set)
14.3.4.3.1	12-Lead ECG: Summary by Visit and Change from Baseline	(Safety Analysis Set)
14.3.4.3.2	12-Lead ECG: Summary of Overall ECG Interpretation by Visit	(Safety Analysis Set)
14.3.4.3.3	12-Lead ECG: Summary of Noteworthy Changes of QT/QTc Interval by Visit	(Safety Analysis Set)

This document is confidential.

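### SAP 13.2 defines laboratory shifts only as normal versus abnormal, the table index lists no laboratory shift table, and no planned output counts subjects per arm by the size of their highest on-treatment elevation.

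*SAP*

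**What the plan says.** SAP 13.2 plans four laboratory outputs.

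- Continuous results: "Summary statistics of actual values and changes from baseline will be provided for each laboratory parameters by treatment group at each study visit". SAP 8.1 fixes the statistics: "Continuous variables will be summarized using the number of subjects (N), mean, standard deviation (SD), median, minimum, and maximum".
- Categorical results: "Frequencies tables, including numbers and percentages of subjects with normal and abnormal (low vs high), will be presented for laboratory parameters with categorical results".
- Shifts: "Shift tables will also be provided displaying the numbers and percentages of subjects with normal and abnormal results compared with the results at baseline".
- Listings: "Subject data listings of all laboratory data will be provided".

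In SAP 18 the chemistry entries are a summary with change from baseline (14.3.4.1.2.1) and "Blood Chemistry: Proportion of Abnormal Results by Study Visit" (14.3.4.1.2.2). No shift table is indexed for any laboratory panel. The mock shells are in a separate document (SAP 21).

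Neither document gives a toxicity grade, a multiple-of-ULN category or a worst-on-treatment category for laboratory results. Protocol 15.4 asks for means, mean changes and counts outside the normal range at each time point. For the ECG, SAP 13.4 does set graded thresholds: QT/QTc above 450, 480 or 500 msec, and change above 30 or 60 msec.

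Three protocol facts bear on the point.

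- Protocol 5.2.2 says the frequent Phase 1 TEAEs "in single administration were diarrhea, headache, lipase increased, tachycardia, and nausea". The repeated-dosing list in the same section does not name lipase.
- Exclusion 31 (Protocol 8.2) applies to "Aspartate aminotransaminase or alanine aminotransaminase" only at 2 x ULN or above, at Screening. It names neither lipase nor amylase.
- Both enzymes are in the chemistry panel (Protocol Table 2), which is drawn at every visit (Protocol Table 1).

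**The concern.** A shift table should show how many subjects got worse and by how much, relative to where each began. With two categories it answers only whether a subject crossed the limit of normal. That loses information in two places. Subjects above ULN at baseline have no worse cell to move to. Among subjects normal at baseline, every rise past the limit looks the same, whatever its size.

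This matters more for some analytes than others. Increased lipase was a frequent finding after single doses in Phase 1, and the entry rules let in subjects with raised transaminases, lipase or amylase. The trial is also meant to inform the dosing regimens of the next study (Protocol 5.4), so a comparison of arms by size of elevation would be useful. As the plan stands, a reader wanting the number of subjects per arm who exceeded a given multiple of ULN would have to build it from the listings.

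**Working it through.** The documents give no figure to reproduce, so the check applies the stated category rules to example values.

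**1. Classification.** Values are multiples of ULN and the examples are illustrative. The last column uses assumed bands (<=1, >1-3, >3-5, >5).

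| Baseline to on-treatment | Normal/abnormal | Low/normal/high | ULN bands |
|---|---|---|---|
| 0.9 to 1.05 | normal to abnormal | normal to high | <=1 to >1-3 |
| 0.9 to 9.0 | normal to abnormal | normal to high | <=1 to >5 |
| 1.5 to 1.6 | abnormal to abnormal | high to high | >1-3 to >1-3 |
| 1.5 to 15 | abnormal to abnormal | high to high | >1-3 to >5 |

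The SAP's wording merges rows 1 and 2, and rows 3 and 4. Splitting abnormal into low and high, as the frequency tables do, changes neither result. The bands separate both pairs.

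**2. What the continuous summary shows.** Effect of one subject on the mean change of an arm of 25 (arm size from the sample size section):

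- 0.9 to 9.0: (9.0 - 0.9) / 25 = 8.1 / 25 = 0.324 x ULN; that subject's change is +8.1 x ULN.
- 1.5 to 15: (15 - 1.5) / 25 = 13.5 / 25 = 0.54 x ULN; that subject's change is +13.5 x ULN.

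The maximum at that visit would therefore show the rise whatever the baseline status. It would not show how many subjects in the arm had a large rise.

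**3. How many subjects enter raised.** The documents give no prevalence, so p is assumed at 2% to 15%. Expected number per arm = 25p. Probability of at least one in an arm = 1 - (1 - p)^25.

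| Assumed p | Expected per arm | P(at least one) |
|---|---|---|
| 2% | 0.5 | 0.40 |
| 5% | 1.25 | 0.72 |
| 10% | 2.5 | 0.93 |
| 15% | 3.75 | 0.98 |

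**4. Does another output give the count by size?**

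- Change summaries: by visit, so peaks at different visits are not combined within a subject.
- Adverse events: a result becomes an event when the investigator judges it clinically significant (Protocol 12.5). Severity is then graded by interference with daily activities (Protocol Table 3), not by the laboratory value.
- Listings: individual values and reference ranges, with no counts. SAP 20 also assigns the chemistry listing to the FAS, so a dosed subject with no evaluable post-baseline PASI assessment would be left out of it as indexed.

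None of them does.

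**The case against.** The strongest reply is that the shift table is one output among several. A reader of SAP 13.2 alone might infer that a subject raised at entry can never register as worse, or that a dose-related rise would look flat across arms. The documents do not support either. Change from baseline is summarised by arm and visit with mean, median and maximum, and does not depend on baseline status; a dose-related rise is what that summary is designed to show. All laboratory data are to be listed, reference ranges have their own listing (16.2.8.1.1), and clinically significant results enter the TEAE tables. This part of the reply stands.

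Three other inferences also go too far.

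- That lipase is the one laboratory effect known in humans. Protocol 5.2.2 lists frequent TEAEs, not laboratory results, and refers to the investigator's brochure for more. Frequent there means more than two subjects, and lipase appears only in the single-dose list, whereas this trial doses for 16 weeks.
- That subjects abnormal at entry contribute nothing to the shift table. They can move to normal; they only cannot show upward worsening.
- That the final table will certainly have just two categories. The sentence before splits abnormal into low and high, and the shells are not available. That split would still leave high to higher unseen.

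Finally, SAP 13.2 meets the protocol's requirement, and ULN bands come from neither document. This is therefore an improvement to reporting, not a breach of the protocol.

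**Conclusion.** The point holds, at low severity. As worded, the shift and proportion-abnormal tables cannot separate high from higher or a marginal rise from a tenfold one. SAP 13.2 promises shift tables that SAP 18 does not list. No planned output counts subjects per arm by the size of their highest on-treatment elevation.

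The conclusion rests on the SAP's text and index, since the shells could not be seen. It does not depend on the assumed 2% to 15% prevalence of raised baselines, which only scales how many subjects the first limitation touches (0.5 to 3.75 per arm of 25). The second limitation applies to subjects normal at entry as well. The primary analysis and clinical management are unaffected.

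**What to change.** In SAP 13.2, define the shift table for lipase, amylase, ALT, AST and bilirubin as baseline category against highest on-treatment category in multiples of ULN, by arm, on the Safety Analysis Set. The sponsor should settle the bands, which may differ by analyte. The text should also say what counts as on-treatment and whether unscheduled results are included. For the other analytes, define the shift as low, normal or high against baseline. Add all of these tables to SAP 18. The bands are for tabulation only and set no management rule.

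The cost is a few lines of SAP text, one new table for the five analytes, and index entries for shift tables already promised. The laboratory values and reference ranges are already planned to be available, so no new data are needed.

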### 13.3. Vital Signs

Vital signs (body temperature, body weight, respiratory rate, heart rate, systolic and diastolic blood pressure measurements) will be evaluated at the visits indicated in the Schedule of Assessments ([Table 1](#)). Summary statistics for actual values and changes from baseline in vital signs will be provided for each

This document is confidential.

vital sign parameter at each scheduled visit by treatment group and overall. A subject data listing of all vital sign data will be provided.

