The potential risks of ME3183 can be estimated based on the AE profile of apremilast (a PDE4 inhibitor) presented in the commercial labeling. The common AEs include diarrhea, nausea, vomiting, depression, weight decrease, upper respiratory tract infection, nasopharyngitis, abdominal pain upper, and headache (Otezla package insert, USA, revised: 04/2020). Also, the most common side effects of known oral PDE4 inhibitors are gastrointestinal (GI) effects such as nausea, vomiting, and diarrhea.⁽⁷⁾ Additionally, GI motility disorder, inflammatory findings including arteritis/vasculitis, and QTc prolongation were reported based on the nonclinical studies.

The potential side effects identified in ME3183 nonclinical studies and also in studies involving other oral PDE4 inhibitors will be carefully monitored in the current study. The GI motility disorder will be identified by monitoring the subjects for any signs of abdominal discomfort,

abdominal distension, abdominal pain, nausea, vomiting, loss of appetite, and constipation. Besides the above, all subjects will be monitored for any cardiovascular manifestations using vital signs and 12-lead electrocardiograms (ECGs). Drug class potential effects such as weight loss and major depression will be monitored during this study. Weight will be measured at scheduled visits throughout the study to check for any potential excessive weight loss. Subjects with major depression or at risk for suicide will be excluded and suicidal ideation will be assessed at Screening and/or Baseline by Columbia-Suicide Severity Rating Scale (C-SSRS).

Considering the above safety profile of ME3183, caution will be exercised (investigator's judgement) before randomizing subjects with any clinically significant (CS) comorbidities (cardiovascular, GI, neurological, etc.). See [Section 8](#) for detailed list of inclusion and exclusion criteria.

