15.4 Safety Analyses

All safety analyses will be performed using the safety analysis set. All recorded AE and SAEs will be listed and tabulated by Medical Dictionary for Regulatory Activities (version 24.1 or higher) system organ class, preferred term, and treatment group over the 16-week Treatment Period and the 4-week Follow-up Period.

The incidence of TEAEs (events with onset dates on or after the first dose of the study drug or that was present prior to dosing and exacerbates after the first dose of study drug) will be included in incidence tables. Events with missing onset dates will be included as TEAEs. If a subject experiences more than 1 occurrence of the same AE, the occurrence with the greatest severity and the closest association with the study drug will be used in the summary tables. SAEs and AEs causing study discontinuation will be tabulated. All AEs will be listed by subject, along with information regarding onset, duration, relationship and severity to study drug, seriousness, action taken with study drug, treatment of event, and outcome.

Vital signs and safety laboratory results will be listed and summarized by treatment group over the 16-week Treatment Period and the 4-week Follow-up Period. Summaries will be provided using descriptive statistics, including mean values and mean change from Baseline values, as well as numbers of subjects with values outside limits of the normal range at each time point.

Any CS physical examination findings and safety laboratory results will be summarized. ECG readings will be evaluated by the investigator and abnormalities, if present, will be summarized and listed. The clinically noteworthy QT/QTc interval (> 450 , > 480 , or > 500 msec) or clinically noteworthy change from Baseline (> 30 or > 60 msec) will also be summarized using descriptive statistics.

Summary tables will be provided for concomitant medications initiated during the study period.

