## **14. Changes from Analysis Planned in Protocol**

There are no changes from analysis planned in the study protocol.

This document is confidential.

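### The SAP omits, without declaring it, the protocol's counts of subjects with out-of-range vital signs, so the number affected per arm is not tabulated

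*SAP*

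**What the plan says.** Protocol 15.4 treats vital signs and laboratory results together: "Vital signs and safety laboratory results will be listed and summarized by treatment group". It then specifies descriptive summaries of values and changes, "as well as numbers of subjects with values outside limits of the normal range at each time point". The synopsis carries the same requirement.

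SAP 13.3 plans less: "Summary statistics for actual values and changes from baseline in vital signs will be provided for each" vital-sign parameter, by scheduled visit, by treatment group and overall, plus a subject listing. SAP 8.1 says what such a summary contains: "Continuous variables will be summarized using the number of subjects (N), mean, standard deviation (SD), median, minimum, and maximum". The only vital-signs table in SAP 18 is 14.3.4.2, "Summary of Vital Signs by Visit and Change from Baseline".

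SAP 14 states: "There are no changes from analysis planned in the study protocol". The opening of Protocol Section 15 says that the SAP prevails where the two documents differ.

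On purpose, Protocol 5.3 assigns cardiovascular monitoring to vital signs and ECGs. It names weight loss as a possible class effect and says: "Weight will be measured at scheduled visits throughout the study to check for any potential excessive weight loss".

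**The concern.** The omission is specific to vital signs. Laboratory data keep abnormal-result tables, and QT/QTc keeps its threshold frequencies. The protocol's count for vital signs has no counterpart in the SAP, and SAP 14 tells the reader that nothing changed. Anyone programming from the SAP would not produce it, and anyone reading SAP 14 would not know it had gone.

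At stake is the safety description by dose. The groups have 25 subjects each, and Protocol 5.4 says the results will inform the design and dosing regimens of the next study. In arms of this size, the number of individuals with an abnormal heart rate or blood pressure is an informative summary, and the protocol asked for it.

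**Working it through.** No planned figure needs to be reproduced: the point rests on no power or alpha calculation, and the protocol made no formal sample size calculation. The check is a comparison of texts, followed by a small illustration of what the planned table can and cannot show.

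**Step 1: safety domains side by side**

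| Domain | Protocol 15.4 | SAP text | SAP 18 tables |
|---|---|---|---|
| Laboratory | Descriptive statistics plus out-of-range counts | 13.2: statistics, normal/abnormal frequencies, shifts | Includes, for example, "Blood Chemistry: Proportion of Abnormal Results by Study Visit" |
| QT/QTc | Threshold categories | 13.4: frequencies by group and visit | 14.3.4.3.3 |
| Vital signs | Descriptive statistics plus out-of-range counts | 13.3: statistics and a listing | 14.3.4.2 only |

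SAP 7.3 shows the same pattern. It defines binary abnormality variables for ECG and laboratory findings, but only continuous change variables for vital signs.

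**Step 2: can the planned statistics supply the count?** Assumptions, not from the documents: k subjects in an arm each lose 8 kg and the others do not change. The arm size of 25 is from SAP 4.3.

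- Mean change = -8k/25.
- SD = square root of [64 × k(25 - k)/25 ÷ 24].

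| k | Share of arm | Mean (kg) | SD (kg) | Median (kg) | Minimum (kg) |
|---|---|---|---|---|---|
| 1 | 4% | -0.32 | 1.60 | 0 | -8.0 |
| 2 | 8% | -0.64 | 2.22 | 0 | -8.0 |
| 3 | 12% | -0.96 | 2.65 | 0 | -8.0 |

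The minimum shows that a large loss occurred in the arm, but it is the same for one, two or three cases. Mean and SD differ here only because every other subject is held at zero. With ordinary variation among the rest, they do not identify k.

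**Step 3: how well does one extreme value separate true rates?** The chance of at least one case in 25 is 1 - (1 - p)^25. For assumed rates of 4%, 8%, 12% and 20% it is 64%, 88%, 96% and 99.6%. An extreme minimum is therefore likely across a fivefold range of rates.

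**Step 4: body weight.** Neither document gives a normal range for body weight or a cut-off for excessive loss. Entry BMI runs from 18.5 to below 40. At an assumed height of 1.70 m (height squared 2.89), that is 18.5 × 2.89 = 53 kg to 40 × 2.89 = 116 kg. A 5 kg loss is then 5/53 = 9% at one end and 5/116 = 4% at the other. Neither a normal-range count nor a minimum change in kg shows proportional loss, and SAP 13.3 plans no percent change for weight.

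**The case against.** The strongest reply is that little is hidden, and much of it stands.

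- A reader might infer that vital signs are reported only as means, so that outliers would look like noise. SAP 8.1 does not support that: SD, median, minimum and maximum are given for values and changes, by arm and visit. In Step 2 the planned table prints the -8 kg.
- A reader might infer that outliers cannot be seen by arm. That is also too strong. Protocol 12.2 requires confirmed clinically significant vital-sign values to be recorded as adverse events, which are tabulated by arm. The vital-signs listing is sorted by treatment group and is readable at 25 per arm. SAP 13.4 also summarises ECG ventricular rate.
- A reader might infer that dropping the counts is what obscures excessive weight loss. It is not, because a normal-range count would not show it. Protocol 5.3 commits to measuring weight at scheduled visits, and the schedule does that. Neither document promises a weight-loss category.
- A reader might infer that the dose decision turns on threshold counts, or that tachycardia is an established repeat-dose signal. No threshold rule exists. Protocol 5.2.2 lists tachycardia among frequent events after single dosing, where frequent means more than two subjects, but not among the frequent events after repeated dosing.

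These routes still do not replace the count. The adverse-event route captures only values confirmed and judged clinically significant, and Protocol 12.2 leaves repeat measurement of out-of-range values to the investigator's discretion. The protocol's count has no such filter. A listing is not a summary. The vital-signs listing is also indexed in SAP 20 to the Full Analysis Set, which requires an evaluable post-baseline time point for the primary endpoint. A dosed subject without one would be absent, although SAP 13 assigns safety analyses to the Safety Analysis Set.

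It might also be said that normal limits are a laboratory concept. But the protocol sentence covers both domains, and Protocol 12.2 itself speaks of out-of-range vital signs.

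**Conclusion.** The point holds as an undeclared departure from the protocol. SAP 13.3 and the table index leave out the by-visit counts of subjects with out-of-range vital signs that Protocol 15.4 specifies, and SAP 14 is incorrect in declaring no changes. This rests on the text alone and needs no assumption.

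The consequence is moderate: extremes remain visible by arm, but the number and percentage of subjects affected are not tabulated. Efficacy analyses are untouched. The 8 kg losses, the assumed rates and the 1.70 m height are illustrative and come from neither document; the conclusion does not depend on them.

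The absence of a weight-loss category is a separate and weaker point. It is a gap between the stated reason for measuring weight and the planned display, not a breach of 15.4.

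**What to change.** 1. In SAP 13.3 and SAP 18, add one table on the Safety Analysis Set, by treatment group and visit. It should give the number and percent of subjects with heart rate, systolic or diastolic blood pressure, respiratory rate or temperature outside normal limits. State the limits in the SAP, since neither document defines them and the table cannot be programmed without them.
2. Correct SAP 14. If the sponsor prefers to keep the omission, declare and justify it there.
3. As a separate option that 15.4 does not require, tabulate by arm prespecified descriptive categories of percent weight loss from Baseline, for example at least 5% and at least 10%. These cut-offs are a reporting choice; neither document supplies them, and they imply no rule for managing subjects.

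The cost is one table for item 1, one more if item 3 is adopted, and a few lines of SAP text. Vital signs, including weight, are already collected at every visit. The downside of item 3 is an extra descriptive table whose cut-offs have no source in the protocol.
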